7.4.2. Liver Biochemistry Assessments for Potential Hepatic Injury or Hepatic Decompensation

[figure not shown]
Liver biochemistry will be assessed to evaluate biochemical triggers that will prompt an immediate reevaluation of patients for potential hepatic injury or hepatic decompensation. These assessments will be performed at:

- Each protocol-specified visit (Table 1)
- Unscheduled visits as needed in the event of signs or symptoms of suspected hepatic injury or decompensation or if laboratory alerts have been triggered

It is important that the laboratory assessments be completed as required and that the central laboratory be used for assessments whenever possible. In the event that a patient cannot return to the clinic for a scheduled or unscheduled visit, or there is an event that triggers a need for an immediate assessment, the use of a local lab is permissible at the discretion of the Investigator. In these cases, the Investigator will obtain the laboratory results and the laboratory normal ranges.

The process for assessing criteria is presented in Figure 2, and the specific threshold(s) for each laboratory analyte to trigger mandatory repeat testing and, potentially, a complete patient evaluation (depending on the repeat result) are summarized in Table 3.

Figure 2: DILI Management Algorithm

DILI = drug-induced liver injury; IP = Investigational Product

NOTE Other laboratory criteria include: ALT, AST, total bilirubin, INR, and electrolytes (sodium).

Table 3: Liver Laboratory Criteria for Monitoring of Suspected Hepatic Injury or Potential Hepatic Decompensation and Criteria for Interruption or Discontinuation of Investigational Product

Laboratory Criteria for Monitoring Suspected Hepatic Injury		
Laboratory Parameter	Action Taken	Rechallenging Criteria
Total Bilirubin		If a patient interrupts IP, they may be rechallenged after a minimum of 30 days if fully resolved OR stable and approved by the Medical Monitor and Investigator.
Baseline \leq ULN and \geq 3x baseline	Interrupt IP	
Baseline $>$ ULN and \geq 2x Baseline	Interrupt IP	
ALT or AST		
$>$ 3x baseline (and $>$ ULN)	Interrupt IP	
\geq 2x baseline	Repeat Test in 2 to 3 days, interrupt IP if still elevated	
Electrolytes^a		
Sodium $<$ 130 mEq/L	Repeat Test in 2 to 3 days, interrupt IP if still below limit	
Laboratory Criteria for Monitoring Potential Hepatic Decompensation (Absence of Clinical Symptoms)		

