Total Bilirubin	Closely monitor until normalization or stabilization. If values continue to increase relative to the baseline value, interrupt IP.	The patient may be rechallenged after a minimum of 30 days if fully resolved OR stable and approved by the Medical Monitor and Investigator. If laboratory values do not normalize, IP should not be restarted.
Baseline \leq ULN and 1.5 mg/dL increase from baseline Baseline $>$ ULN and 1.0 mg/dL increase from baseline		
INR^b	Closely monitor until normalization or stabilization. If values continue to increase relative to the baseline value, interrupt IP.	The patient may be rechallenged after a minimum of 30 days if fully resolved OR stable and approved by the Medical Monitor and Investigator. If laboratory values do not normalize, IP should not be restarted.
$>$ 0.3 increase from baseline		
\geq 2.0 unless due to vitamin K deficiency	Discontinue IP permanently	Continue to return for scheduled study visits for safety follow up. Monitor closely for clinical outcomes per protocol.
Laboratory Criteria for Monitoring Potential Hepatic Decompensation in the Presence of Clinical Symptoms		
Total bilirubin thresholds defined in Part B OR an INR increase from baseline of \geq 1.5 are observed in the presence of clinical symptoms of cholestatic hepatitis or hepatic encephalopathy ^c	Discontinue IP permanently	Continue to return for scheduled study visits for safety follow up. Monitor closely for clinical outcomes per protocol.

IP = investigational product

^a Sodium will be measured as an assessment of liver failure (hyponatremia).

^b Does not apply in patients on anti-coagulants.

^c Symptoms of cholestatic hepatitis includes dark urine and jaundice. Symptoms of hepatic encephalopathy may include lack of awareness, shortened attention span, lethargy, gross disorientation, or coma (unresponsive to verbal or noxious stimuli).

It should be noted that it is difficult to recognize every potential marker of hepatic or renal deterioration. There is no substitute for good medical judgment. Investigators will be reminded to be cautious and mindful in their evaluation of patients' symptoms, signs, and laboratory results. However, for example, a single abnormal laboratory analyte result may be artefactual; accordingly, Investigators will be allowed to implement an alternate follow-up procedure if considered appropriate based on their medical judgement, but only after documented agreement with the Sponsor's Medical Monitor.

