7.6. Close Observation

If investigational product is interrupted or discontinued as described in [Section 8.4](#), patients should be closely monitored (contacted by the site a minimum of every 2 weeks and scheduled visits every 6 weeks; if returning to the site for a scheduled visit is not feasible, use of a local lab may be permissible at the Investigator's discretion). At a minimum, the following assessments should be conducted at each study visit:

- Physical exam and thorough review of patient reported signs and symptoms,
- Liver biochemistry (including ALP, ALT, AST, GGT, total and conjugated bilirubin, creatinine, and albumin), prothrombin time (PT)/INR, serum electrolytes, and assessment of Child Pugh (only if the patient is at the study site) and MELD scores.

In addition, a trough pharmacokinetic sample for assessment of OCA serum drug levels and its major metabolites should be obtained in any patient who develops an AE that is indicative of or consistent with hepatic injury or decompensation.

The following additional monitoring procedures should be performed for events of potential hepatic injury (per FDA Guidance for Industry on Drug Induced Liver Injury) or suspected hepatic decompensation based on criteria described in [Section 7.4.1](#), [Section 7.4.2](#), and [Section 7.4.3](#). These cases need to be discussed with the Sponsor's Medical Monitor:

- Repeating liver biochemistry and function tests as described in [Section 7.4.2](#). Frequency of retesting can decrease to once a week or less if abnormalities stabilize or the study drug has been discontinued and the patient is asymptomatic, as clinically indicated.
- Obtaining a more detailed history of symptoms and prior or concurrent diseases.
- Obtaining a history of concomitant drug use (including nonprescription medications and herbal and dietary supplement preparations), alcohol use, recreational drug use, and special diets is important. Concomitant drugs with potential hepatotoxicity should be recorded and discontinued unless alternative therapies are not available. In the case of concomitant drugs potentially hepatotoxic, continued use of investigational

product should be discussed with the Sponsor's Medical Monitor. The patient may be discontinued from investigational product, if clinically appropriate.

- Obtaining a history of exposure to environmental chemical agents or herbal supplements which may be associated with liver toxicity.

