8.4. Dose Adjustment, Interruption, and Withdrawal from Investigational Product or Study

Investigational product may be temporarily decreased (eg, from 10 mg twice weekly to 5 mg twice weekly, or from 5 mg twice weekly to 5 mg once weekly) or temporarily or permanently stopped based on tolerability concerns. Investigational product may be resumed at the maintenance dose upon resolution of gastroenteritis or worsening renal function or dehydration if there is no evidence of liver injury. For rechallenge following all other dose interruptions (see Table 5), investigational product should be initiated at a lower dose and patients monitored more frequently with up-titration considered based on tolerability.

Adjustments, interruptions, discontinuation, and any rechallenge of investigational product should be implemented per the criteria outlined in Table 5. Patients that discontinue investigational product are expected to continue in the study (and follow the regular visit schedule, with the exception of PK sampling [trough PK may be required in the event of an AE consistent with hepatic injury or decompensation]) until the end of the study, but may withdraw consent at any time.

Table 5: Criteria for Dose Adjustment, Interruption, Discontinuation, and Rechallenge

DOSE ADJUSTMENT		
Criteria	Action Taken with IP	Adjustment
New Onset Severe Pruritus	Drug holiday or less frequent dosing	Return to original dose regimen if tolerated
DOSE INTERRUPTION		
Criteria	Action Taken with IP^a	Rechallenge^b
If liver biochemistries indicative of suspected hepatic injury are identified as exceeding upper threshold criteria and require immediate interruption (see Part A of Table 3) ^c	Interrupt immediately upon initial observation	Patient may be rechallenged after a minimum of 30 days if fully resolved OR stable and approved by the Medical Monitor and Investigator.
Other liver biochemistries indicative of suspected hepatic injury are outside upper threshold criteria upon repeat testing as defined in Part A of Table 3 ^d	Interrupt after confirmation by repeat testing	
Liver biochemistries indicative of potential hepatic decompensation in the absence of symptoms (see Part B of Table 3) ^e	Closely monitor until normalization or stabilization. If values continue to increase relative to the baseline value, interrupt	

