Clinical events indicative of hepatic decompensation (see Part B of Table 4)	Closely monitor until normalization or stabilization	The patient may be rechallenged after a minimum of 30 days if fully resolved OR stable and approved by the Medical Monitor and Investigator. IP should be re-initiated at a lower dose (or lower dose frequency) and titrated per Investigator discretion.
Gastroenteritis (established severe abdominal pain, vomiting, diarrhea for more than 4 days)	Interrupt	If no evidence of liver injury is detected, IP may be restarted at the same dose after resolution of intercurrent illness.
Evidence of worsening of renal function or dehydration	Interrupt	
DOSE DISCONTINUATION		
Criteria	Action Taken with IP	Rechallenge
If INR increases ≥ 2.0 in absence of clinical symptoms criteria (unless due to vitamin K deficiency) ^f	Discontinue / No Rechallenge	Discontinue IP permanently and continue to return for scheduled study visits for safety follow-up.
If total bilirubin thresholds (Part B of Table 3) are observed in the presence of clinical symptoms of cholestatic hepatitis or hepatic encephalopathy ^f		Continue to return for scheduled study visits for safety follow-up. Monitor closely for clinical outcomes according to protocol assessments.
Multi-Organ failure requiring hospitalization		
Liver transplantation		
Pregnancy		

Fully resolved = Return to baseline levels or return to within normal limits (WNL). IP = investigational product

^a If patient is unable to be evaluated promptly, study drug must be immediately interrupted.

^b Requires complete documentation of complete resolution or normal/baseline results based on laboratory parameters and symptoms.

^c Total bilirubin baseline \leq ULN and $\geq 3x$ baseline, baseline $>$ ULN and $\geq 2x$ baseline, ALT or AST $> 3x$ baseline (and $>$ ULN)

^d ALT or AST $\geq 2x$ baseline or electrolytes (sodium $<$ 130 mEq/L).

^e Total bilirubin baseline \leq ULN and 1.5 mg/dL increase from baseline OR baseline $>$ ULN and 1.0 mg/dL increase from baseline; INR $>$ 0.3 increase from baseline

^f If INR increases ≥ 2.0 in the absence of clinical symptoms or if or total bilirubin thresholds OR an INR increase from baseline of ≥ 1.5 are observed in the presence of clinical symptoms of cholestatic hepatitis or hepatic encephalopathy.

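### When baseline ALT or AST is at or below half the ULN, a value that has fallen back into the normal range can count as fully resolved in Table 5 while still meeting the Table 3 interruption trigger

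*Protocol*

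**What the plan says.** **Stopping.** Table 3 (Section 7.4.2) has two ALT/AST tiers under suspected hepatic injury, the block that Table 5 calls Part A. Above 3x baseline and above the ULN, drug is interrupted at once. At 2x baseline or more the instruction is "Repeat Test in 2 to 3 days, interrupt IP if still elevated". This second tier carries no ULN condition. Table 5 (Section 8.4) restates it as "Other liver biochemistries indicative of suspected hepatic injury are outside upper threshold criteria upon repeat testing as defined in Part A of Table 3", and its footnote d gives the ALT/AST limit as at least 2x baseline, again without the ULN. For total bilirubin with baseline at or below the ULN, the Part A trigger is at least 3x baseline.

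**Restarting.** The Table 5 rechallenge column reads "Patient may be rechallenged after a minimum of 30 days if fully resolved OR stable and approved by the Medical Monitor and Investigator". The table notes give "Fully resolved = Return to baseline levels or return to within normal limits (WNL". Footnote b sets the documentation: "Requires complete documentation of complete resolution or normal/baseline results based on laboratory parameters and symptoms".

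**Conditions at restart.** Section 8.4 says that, after interruptions of this kind, "investigational product should be initiated at a lower dose and patients monitored more frequently with up-titration considered based on tolerability". Section 7.6 says of potential hepatic injury cases: "These cases need to be discussed with the Sponsor's Medical Monitor".

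**The concern.** A restart criterion should not be satisfied by a value that is still a reason to stop. Here the stop rule is relative to the patient's own baseline, while one limb of the restart rule is relative to the laboratory range. For a patient whose baseline sits low in that range, the two rules overlap.

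Liver biochemistry is assessed at every protocol-specified visit (Section 7.4.2). A patient restarted inside the overlap whose value does not change would meet the repeat-test trigger again at the next visit and, if confirmed, be interrupted again.

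The route also matters. If approval by the Medical Monitor and Investigator belongs only to the stable alternative, such a patient could restart as fully resolved without it. Section 7.6 requires discussion with the Medical Monitor, which is not the same as approval. The population is Child-Pugh B and C, for whom Section 5.5 stresses the raised risk of decompensation.

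**Working it through.** The protocol states no figure to reproduce, so this is a check of two rules against each other. Let b be baseline and v the current value, both in multiples of the ULN, and let a value equal to the ULN count as normal.

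**ALT/AST**
- Stop on repeat testing (Table 3; Table 5 footnote d): v ≥ 2b.
- Fully resolved (Table 5 notes): v ≤ b or v ≤ 1.
- Both hold when 2b ≤ v ≤ 1, which is possible only if b ≤ 0.5.

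| Baseline (x ULN) | Values meeting both rules (x ULN) |
|---|---|
| 0.25 | 0.50 to 1.00 |
| 0.30 | 0.60 to 1.00 |
| 0.40 | 0.80 to 1.00 |
| 0.50 | 1.00 only |
| above 0.50 | none |

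**Total bilirubin, baseline at or below the ULN**
- Stop: v ≥ 3b. Both rules hold when 3b ≤ v ≤ 1, so only if b ≤ 1/3.
- Overlap: b = 0.20 gives 0.60 to 1.00; 0.25 gives 0.75 to 1.00; 0.30 gives 0.90 to 1.00; 1/3 gives 1.00 only; above 1/3, none.

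**Rows whose own trigger cannot be met by a normal value**
- The ALT/AST tier above 3x baseline, because it also requires v > 1.
- Bilirubin with baseline above the ULN, because 2b > 1.
- The Part B bilirubin rise of 1.5 mg/dL. With an assumed ULN of 1.0 to 1.3 mg/dL, baseline would have to be at or below 1.0 − 1.5 = −0.5 to 1.3 − 1.5 = −0.2 mg/dL.

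**Worked case, assumed ULN 40 U/L, baseline 15 U/L.** Here 2b = 30 and 3b = 45.
1. A value of 46 exceeds both 45 and 40, so drug is interrupted at once.
2. The value later falls to 31. Since 31 ≤ 40, it has returned to the normal range and is fully resolved.
3. Since 31 ≥ 30, it still meets the repeat-test trigger.

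**Scale of the baseline limit.** The protocol gives no ULNs. Over an assumed ULN of 30 to 55 U/L, the ALT/AST limit is 0.5 × 30 = 15 to 0.5 × 55 = 27.5 U/L. Over 1.0 to 1.3 mg/dL, the bilirubin limit is 1.0/3 = 0.33 to 1.3/3 = 0.43 mg/dL.

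**Does anything close the gap?** Footnote b accepts normal or baseline results. I found no text that requires a value below the trigger before restart or that resets baseline. Sections 8.2 and 8.3 set no lower limit for ALT or AST, so baselines in the affected range are not ruled out.

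**The case against.** **Restart at trigger level is allowed anyway.** The stable and approved alternative has no requirement to be below the trigger. This stands: the fix secures an approval step and does not ban restart.

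**Approval may already apply.** The rechallenge sentence can be read with approval covering both alternatives. This stands as an ambiguity. A reader might infer that the protocol plainly permits unapproved restart; the wording does not settle that.

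**A value that never left the range has not returned to it.** A reader might infer that any in-range value of 2x baseline or more is at once a reason to stop and fully resolved. Footnote b, read literally, supports this because it speaks only of normal or baseline results. But it governs documentation and also refers to symptoms, and the definition itself says return. That case is disputable. The case of a value that exceeded the ULN and came back needs no such reading.

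**Still elevated might mean above the ULN.** That would remove the ALT/AST overlap at the stop side, but Table 5 and footnote d tie the repeat test to the threshold of 2x baseline. This does not stand.

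**There are safeguards.** Restart is optional, at least 30 days later, at a lower dose and with closer monitoring. The case must be discussed with the Medical Monitor, and Section 7.4.2 allows alternate follow-up "but only after documented agreement with the Sponsor's Medical Monitor". Table 3 continues to apply after restart. These stand and limit the consequence, although none of them changes the definition.

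**The trigger may be the loose side.** Adding the ULN condition to the 2x row would also empty the ALT/AST overlap, and the protocol does not show which was intended. That is fair, but it would relax a safety trigger and leave bilirubin untouched.

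**Conclusion.** The definition is wrong as written for a limited group: baseline ALT or AST at or below 0.5x ULN, or bilirubin at or below one third of the ULN. In that group, a value that caused interruption and has come back into range can be fully resolved and still meet a Part A trigger. The bounds follow from the rules themselves; only the conversions to U/L and mg/dL rest on assumed ULNs. The bilirubin case is probably rare in Child-Pugh B and C disease.

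Severity is minor. A reader might infer a material hazard, a large affected group or an effect on the primary PK and safety analyses. The protocol supports none of these: the safeguards at restart are real, the number of patients below the limits is not derivable, and no analysis depends on this definition in any way that the document shows.

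**What to change.** Leave all thresholds in Table 3 and in Table 5 footnotes c and d unchanged. In the Table 5 notes write:

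*Fully resolved = back at baseline level, or back within normal limits and no longer meeting any Table 3 Part A interruption criterion for that analyte.*

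In footnote b add:

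*For rechallenge as fully resolved, normal results must also no longer meet any Table 3 Part A interruption criterion for that analyte.*

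Wording by analyte catches the patient interrupted above 3x baseline whose value settles in range at 2x or more. Limiting the footnote b clause to the fully resolved route leaves the stable and approved route as it is.

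The cost is one clause in two notes, with no change to visits, sampling or stop rules. The downside is that a patient with a lasting in-range value at trigger level can restart only as stable, with approval by the Medical Monitor and Investigator. Patients with baseline ALT/AST above 0.5x ULN and bilirubin above one third of the ULN are unaffected on those analytes.

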8.4.1. Other Reasons for Discontinuation of Study or Investigational Product

The following events are considered appropriate reasons for a patient to discontinue investigational product; however, these patients are expected to continue in the study until study termination (or at the discretion of the Sponsor):

- Patient begins treatment with commercially available OCA.
- The Investigator or Sponsor considers that it is advisable or in the best interest of the patient.

- The occurrence of clinical or laboratory AEs considered by the Investigator to be clinically important safety concerns and related to study drug.
- Withdrawal of consent
 - Consent may be fully withdrawn (in which case the patient discontinues both investigational product and study visits and procedures).
 - Consent may be modified to discontinue study visits but allow semi-annual telephone contact.
 - Consent may be modified to discontinue study visits or semi-annual telephone contact but allow continued access to medical records to assess for suspected major adverse cardiovascular events (MACE) and liver-related clinical events.
 - Early termination procedures should be conducted if the patient withdraws consent (see [Section 9.7.13](#)).

The Investigator is encouraged to contact the Sponsor prior to discontinuing a patient from treatment. The Investigator must notify the Sponsor study monitor by telephone or email as soon as possible if any patient prematurely withdraws from the study.

8.4.1.1. Withdrawal of Consent to Continue in the Study

If the patient decides that it is in his/her best interest to discontinue from the study, he or she may withdraw consent. It is fully understood that all patients volunteer for the study and that they may withdraw their consent to continue in the study at any time.

Early termination procedures should be conducted if the patient withdraws consent (See [Section 9.7.13](#)).

A reasonable effort must be made to determine the reason(s) for patient discontinuation. This information and date must be recorded in the appropriate eCRF.

8.4.1.2. Lost to Follow-Up

Patients will be considered “lost to follow-up” only after documented attempts to reach the patient prove unsuccessful. A reasonable effort (ie, 2 phone calls/messages, no response to registered letter) must be made to contact the patient and determine the reason(s) why a patient fails to return for a study visit or is lost to follow-up. This information and date of contact must be recorded in the appropriate eCRF.

8.4.2. Patient Discontinuation Notification

The Investigator must notify the Sponsor as soon as possible if any patient prematurely discontinues from the study. The date when the patient is withdrawn and the primary reason(s) for discontinuation must be recorded in the eCRF; additional information may be requested by the Sponsor to complete a discontinuation narrative. This information must be documented in the eCRF.

If a patient is withdrawn from the study early (regardless of the cause), all of the early termination (ET)/EOS evaluations are to be performed at the time of withdrawal, to the extent possible.

9. TREATMENT OF PATIENTS

9.1. Investigational Product Treatment Regimen

The term investigational product refers to either OCA (provided as part of this clinical study) or placebo.

Two treatment groups will be evaluated: OCA and placebo. Investigational product will be administered orally. Each dose will be made up of 1 tablet (ie, one OCA 5 mg tablet or one OCA 10 mg tablet, or matching placebo).

Investigational product will be taken orally with water for the duration of the study. Patients will be instructed to begin dosing on Day 1 and are to take investigational product at approximately the same time on dosing days. Patients must be instructed to swallow the tablet whole; they must not chew, divide, or crush the tablet.

At each study visit where the dose of investigational product is administered at the site, all assessments, except for the post-dose collection of blood samples for the PK assessment, must be completed before administration of investigational product.

